8.1.1. Laboratory Safety Assessments

Abnormal and clinically significant laboratory tests should be recorded as adverse events. To meet the definition of clinically significant, the test result generally requires a change in medical management (e.g., new medication, unplanned treatment, additional tests, etc.).

8.1.1.1. Hematology, Serum Chemistry, and Coagulation Test

Assessments will be performed at the time points indicated in the Schedule of Assessments ([Table](#)) and analyzed at laboratories where collected. Investigators may have additional blood tests performed for the purpose of planning treatment administration, or for following AEs, as clinically indicated.

- Hematology: Complete blood count (CBC) with differential and platelet count.
- Coagulation: Prothrombin time and International Normalized Ratio (INR).
- Serum Chemistry: Total bilirubin, alanine transaminase (ALT), aspartate transaminase (AST), alkaline phosphatase, lipase, amylase, sodium, potassium, bicarbonate, chloride, calcium, phosphorus, blood urea nitrogen, creatinine, magnesium, thyroid stimulating hormone (TSH), and glucose.
- Patients must agree to use effective contraception during the study and for ≥ 180 days following last dose of study drug (Abemaciclib). The definition of effective contraception is provided in [Section 2.6.1](#) of this protocol.

8.1.1.2. Urinalysis

Urinalysis (without microscopic analysis, unless indicated) will be performed at time points indicated in the Schedule of Assessments ([Table 2](#)) and analyzed by local laboratories. Microscopic analysis, urine protein-creatinine ratio (UPCR), and 24-hour urine collection for protein should be performed as clinically indicated.

8.1.2. Physical Examination

A physical examination including, but not limited to, general appearance, head, eyes, ears, nose, throat, neck, heart, chest, abdomen, musculoskeletal, extremities, skin, lymph nodes, neurological, genitourinary (as appropriate), and rectal (as appropriate) will be assessed at time points indicated within the Schedule of Assessments ([Table 2](#)). The physical examination will include examination of known and suspected sites of disease.

8.1.3. Vital Signs

Heart rate, temperature, blood pressure, respiratory rate, and weight will be assessed at time points indicated within the Schedule of Assessments ([Table 2](#)). Height will be assessed only at the Screening visit. Heart rate, temperature, blood pressure, and respiratory rate will also be assessed during Abemaciclib as described in [Section 4.1.2.2](#) and the footnotes of the Schedule of Assessments ([Table 2](#)).

8.1.4. Performance Status

The ECOG scale will be used to assess performance status at Screening and at time points indicated within the Schedule of Assessments ([Table 2](#)).

8.1.5. Electrocardiogram (ECG)

A single tracing 12-lead tracing will be used for all ECGs. It is preferable that the machine used has a capacity to calculate standard intervals automatically. ECG will be performed at the time points indicated in the Schedule of Assessments ([Table 2](#)) and as clinically indicated throughout the study.

8.2. Adverse Events

All observed or volunteered AEs regardless of suspected causal relationship to study drug (Abemaciclib) will be reported as described below.

8.2.1. Definition of Adverse Event

An AE is any untoward medical occurrence in a trial patient who is administered a drug or biologic (medicinal product); the event may or may not have a causal relationship with the medicinal product. Examples of AEs include, but are not limited to the following:

- Clinically significant symptoms and signs including:
 - Worsening of signs and symptoms of the malignancy under study drug treatment (Note: Disease progression with or without worsening of signs and symptoms assessed by measurement of malignant lesions on radiographs or other methods should not be reported as AEs unless the outcome is fatal during the study or within the safety reporting period for the study.)
 - Signs and symptoms resulting from drug overdose, abuse, misuse, withdrawal, sensitivity, dependency, interaction, or toxicity
 - All treatment-emergent possibly related and unrelated illnesses, including the worsening of a preexisting illness
 - Injury or accidents - Note that if a medical condition is known to have caused the injury or accident (e.g., hip fracture from a fall secondary to dizziness), the

medical condition (dizziness) and the outcome of the accident (hip fracture from a fall) should be reported as 2 separate AEs.

- Symptoms or signs resulting from exposure *in utero*
- Abnormalities in physiological testing or physical examination findings that require clinical intervention or further investigation (beyond ordering a repeat confirmatory test)
- Laboratory abnormalities that meet any of the following criteria (Note: Merely repeating an abnormal test, in the absence of any of the below conditions, does not constitute an AE. Any abnormal test result that is determined to be an error does not require reporting as an AE.)
 - Test result that is associated with accompanying symptoms
 - Test result that requires additional diagnostic testing or medical/surgical intervention
 - Test result that leads to a change in study drug (Abemaciclib) dosing other than protocol-stipulated dose adjustments or discontinuation from the trial, significant additional concomitant drug treatment, or other therapy
 - Test result that is considered to be an AE by the Investigator or ELI LILLY

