In preclinical species, the primary target organs for toxicity (associated with up to 3 months of continuous daily dosing) are bone marrow (resulting in pancytopenia), gastrointestinal tract, lymphoid tissues, and male reproductive tract. All of these changes demonstrated complete or partial reversibility during the recovery period. In humans, the most common ($\geq 10\%$) treatment-emergent adverse events (TEAEs) possibly related to the study drug for patients who received single-agent abemaciclib include diarrhea, nausea, fatigue, neutropenia, vomiting, decreased appetite, leukopenia, thrombocytopenia, anemia, abdominal pain, and blood creatinine increased. Increased rates of skeletal and cardiac variations and malformations, accompanied by decreased fetal weights, were observed in an embryo–fetal development study of abemaciclib in rats.

After determining a recommended dose of 150 mg bid in a phase 1 study ²¹, abemaciclib monotherapy showed superior response rates in the MONARCH-1 study in a heavily pre-treated patient population ²². It has subsequently demonstrated impressive response rates and improvement in PFS in 2 randomized phase 3 studies ^{23,24}. In the neoadjuvant breast cancer setting, the ongoing neoMONARCH Phase 2 open-label, randomized study (I3Y-MC-JPY) showed an acceptable safety profile for abemaciclib (150 mg twice daily) as monotherapy and in combination with anastrozole, with reduction of breast cancer tumor cell proliferation marker (Ki67 index) to a significantly greater extent than anastrozole alone ²⁵. Abemaciclib has been well studied in breast cancer, and common side effects encountered in clinical studies include diarrhea (86%), neutropenia (46%), nausea (45%) and fatigue (40%) ²³, but the major grade 3 or higher side effect remains neutropenia in up to 20% of patients ^{23,24}. Thus patients on CDK4/6 inhibitors require frequent lab checks to monitor development of neutropenia, though the clinical significance of CDK4/6 inhibition – related neutropenia is debatable as the incidence of febrile neutropenia remains very low ²³. More significantly, compared to the 2 other approved CDK4/6 inhibitors, abemaciclib has a significantly reduced incidence of grade 3 or higher neutropenia ²⁶. Thus, abemaciclib represents a significant new option for CDK4/6 inhibition with impressive clinical efficacy and decreased incidence of significant neutropenia.

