Hematologic toxicities including neutropenia, leukopenia, anemia, and thrombocytopenia have been observed in patients treated with abemaciclib, and causality has been established. Severe (Grade 3 and 4) neutropenia was observed in patients receiving abemaciclib. Patients should be monitored closely for signs of infection, anemia, and bleeding. **Table 9 provides guidance on dose modification and management of hematologic toxicities.**

Table 9: Dose Modification and Management — Hematologic Toxicities

Monitor complete blood counts prior to the start of abemaciclib therapy, every 2 weeks for the first 2 months, monthly for the next 2 months, and as clinically indicated.	
CTCAE Grade	Abemaciclib Dose Modifications
Grade 1 or 2	No dose modification is required.
Grade 3	Suspend dose until toxicity resolves to \leq Grade 2. Dose reduction is not required.
Grade 3, recurrent, or Grade 4	Suspend dose until toxicity resolves to \leq Grade 2. Resume at next lower dose.
Patient requires administration of a blood cell growth factor	Suspend abemaciclib dose for at least 48 hours after the last dose of blood cell growth factor and until toxicity resolves to \leq Grade 2. Resume abemaciclib at next lower dose unless the dose was already reduced for the toxicity that led to the use of the growth factor.

General Guidance for Non-hematologic Toxicities (excluding diarrhea, ILD/Pneumonitis and increased ALT/AST) Monitoring

Table 10: Dose Modification and Management — Non-hematologic Toxicities Excluding Diarrhea and ALT Increased

CTCAE Grade	Abemaciclib Dose Modifications
Grade 1 or 2	No dose modification is required.
Persistent or recurrent Grade 2 toxicity that does not resolve with maximal supportive measures within 7 days to baseline or Grade 1	Suspend dose until toxicity resolves to baseline or Grade 1. Resume at next lower dose.
Grade 3 or 4	

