8.3.4. Recording Adverse Events in the Case Report Forms

The Investigator is to report all directly observed AEs and all AEs reported by the study patient. In addition, each study patient will be questioned about AEs. All AEs that meet the criteria specified in [Section 8.2.1](#) are to be recorded on patient source documents and on the CRFs. AEs should be reported using concise medical terminology on the CRFs.

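### Section 8.2.1 exempts protocol-stipulated dose changes while 8.1.1 does not, so asymptomatic cytopenias held under Table 9 may be left out of the AE tables

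*Combined protocol and SAP*

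**What the plan says.** Section 8.2.1 defines an AE broadly and then gives a list introduced by "Examples of AEs include, but are not limited to the following". One item is "Laboratory abnormalities that meet any of the following criteria". Four criteria follow, and any one is enough:

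- the result comes with symptoms;
- the result calls for more diagnostic work or for an intervention;
- the result changes dosing, in these words: "Test result that leads to a change in study drug (Abemaciclib) dosing other than protocol-stipulated dose adjustments or discontinuation from the trial", with added drug treatment or other therapy in the same bullet;
- the investigator or the company considers it an AE.

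A note to this item says that repeating an abnormal test does not by itself make an AE.

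Section 8.3.4 ties recording to this list: "All AEs that meet the criteria specified in" Section 8.2.1 go onto source documents and CRFs. It does not mention Section 8.1.1.

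Section 8.1.1 has its own rule. Abnormal, clinically significant laboratory tests should be recorded as AEs, and to be clinically significant "the test result generally requires a change in medical management (e.g., new medication, unplanned treatment, additional tests, etc". It makes no exception for dose changes that the protocol stipulates.

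Table 9 (Section 6.4.3) suspends abemaciclib for Grade 3 hematologic toxicity. For "Grade 3, recurrent, or Grade 4" it suspends and then resumes at a lower dose. Table 7 does the same for persistent or recurrent Grade 2, or Grade 3, ALT/AST. Table 1 (Section 4.1.1) lists toxicities, some of them laboratory findings, that lead to withdrawal.

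**The concern.** Safety and tolerability are the stated purpose of the trial, and tolerability and feasibility are a secondary objective (Section 3). Section 2.6.1 names neutropenia, raised creatinine and raised AST/ALT as adverse events of special interest, and all three are detected from laboratory values.

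The third laboratory criterion exempts the dose changes that the protocol stipulates, which are the changes these toxicities are most likely to cause. A site that reads 8.2.1 and 8.3.4 together could decide that a held dose is not a reason to enter an AE. A site that reads 8.1.1 could decide the opposite. The AE counts for a secondary objective would then depend partly on recording habit.

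The effect could reach beyond the final tables. The company receives AEs (Section 8.3.2), and routine monitoring of non-serious events works from AEs as recorded in CRFs and source documents (Section 8.4).

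**Working it through.** The plan states no toxicity rate, threshold or safety stopping boundary, so there is no figure to reproduce. The check is mainly textual, with one illustration of size.

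**1. One case through the rules.** A man has asymptomatic Grade 3 neutropenia. Table 9 suspends his drug, the count is repeated and recovers, and he restarts.

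| Rule | Met? |
|---|---|
| 8.2.1, symptoms | No |
| 8.2.1, further testing or intervention | No treatment was given, and the note says a repeat alone is not enough |
| 8.2.1, dosing change | No, the hold is stipulated in Table 9 |
| 8.2.1, investigator or company judgement | Discretionary |
| 8.1.1, change in management | Arguable: a hold changes management, but the rule says generally and one of its examples is treatment that is unplanned |

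No objective criterion in 8.2.1 is met. Recording rests on judgement or on a broad reading of 8.1.1.

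**2. Cases that are better covered.** For ALT/AST, Table 8 lists further hepatic tests, and ordering them may meet the testing criterion. If growth factor is given for neutropenia, the intervention criterion is met. The exposed group is therefore asymptomatic, untreated Grade 3 or 4 cytopenia. Grade 1 and 2 cytopenia is not touched by the clause, because Table 9 requires no dose change there.

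**3. Discontinuation.** In the third criterion, discontinuation from the trial can be read as a second trigger for an AE or as a second item inside the exception. On the latter reading, a laboratory-driven withdrawal under Table 1 would not meet the criterion either.

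**4. What the analysis section recovers.** Section 10.2.2 counts clinically significant laboratory abnormalities, but places them among the types of treatment-emergent AE, so the count inherits the unclear definition. It also summarizes laboratory results descriptively by dose level, which does not commit to patient counts by grade. Section 8.1 does refer to CTCAE grading of laboratory abnormalities, but 10.2.2 specifies no table that shows it.

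**5. Illustration of size.** Inputs:

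- p = 0.20, the upper figure in Section 2.3.2: "the major grade 3 or higher side effect remains neutropenia in up to 20% of patients". It comes from breast cancer studies.
- N = 30, the planned total, reached only if the null hypothesis is rejected at 23 patients (Section 10.1).
- f, the share of these patients whose event is not entered as an AE. The documents give no value, so it runs from 0 to 1 as an assumption.

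Expected patients with the event: N × p = 30 × 0.20 = 6.0. Expected number recorded: N × p × (1 − f).

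| f | Recorded of 30 | Rate |
|---|---|---|
| 0 | 6.0 | 20% |
| 0.25 | 4.5 | 15% |
| 0.50 | 3.0 | 10% |
| 0.75 | 1.5 | 5% |
| 1 | 0 | 0% |

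Exact (Clopper-Pearson) 95% limits are 7.7% to 38.6% for 6/30 and 0% to 11.6% for 0/30. If the trial ends at 23 patients, the expected number is 23 × 0.20 = 4.6, and the recorded number runs from 4.6 down to 0.

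**The case against.** The strongest reply is that the protocol, read as a whole, already treats these results as AEs. The 8.2.1 list gives examples and is open-ended, and the exempting bullet is one of four alternatives. Section 8.1.1 is an operative instruction with no exception. Section 2.6.1 calls neutropenia and raised AST/ALT adverse events of special interest. Section 6.4.3 calls ALT/AST elevation an adverse drug reaction, which Section 8.3.6 defines as a related AE. Sections 6.1.5.1 and 6.4.1 describe dose modifications as responses to AEs, so a stipulated hold presupposes one. The laboratory values are collected and summarized in any case.

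Most of this stands, and it defeats a stronger reading that a reader might infer: that 8.2.1 rules these toxicities out as AEs, so that they go unrecorded and the toxicity rate is understated. The documents do not support that. Failing one criterion does not remove a result from the definition, the values remain in the laboratory data, and no shortfall has been shown.

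The reply does not remove the conflict. The open-ended wording introduces the types of AE; the laboratory item then sets its own criteria and an exclusion note. Section 8.3.4 points to 8.2.1 alone, and the examples in 8.1.1 leave a planned hold open to either reading. That other sections assume these events are AEs is a reason to bring 8.2.1 into line with them.

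**Conclusion.** The inconsistency is real, and its effect is possible but not demonstrated. A stipulated dose change does not by itself make a laboratory result an AE under 8.2.1. This conflicts with 8.1.1 and with the way 6.1.5.1 and 6.4.1 describe dose modification. Asymptomatic, untreated Grade 3 or 4 cytopenias held under Table 9 may be left out of the AE tables, depending on the investigator's reading. ALT/AST is a weaker example, and the status of stipulated discontinuation is unclear.

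The undercount is near zero if 8.1.1 is followed broadly. The ceiling of about 6 in 30 assumes a 20% rate carried over from breast cancer, full enrollment to 30, and every such event being asymptomatic, untreated and left out. The first is an upper figure from another disease, and the last is an extreme.

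Severity is moderate, not must-fix. The primary endpoint, the two-stage decision rule and the dose rules are unaffected.

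**What to change.** 1. In 8.2.1, delete the exception for protocol-stipulated dose adjustments. The bullet should say that any laboratory-driven hold, reduction or discontinuation of abemaciclib is recorded as an AE, including those under the Section 6.4.3 dose-modification tables and Table 1. Cite them this way and not as a number range: two tables are numbered 10 (Sections 6.4.3 and 8.3.5), and Table 8 lists tests. Naming discontinuation outright also settles that ambiguity.
2. Make the definition of clinical significance in 8.1.1 and the recording rule in 8.3.4 refer to this same list.
3. In 10.2.2, add the number and percentage of patients by worst CTCAE grade for neutrophils, platelets, haemoglobin, ALT, AST, bilirubin and creatinine, derived from the laboratory values already collected. These counts do not depend on whether an AE was entered.

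The cost is a wording amendment, one added table, a few more AE entries and somewhat less favourable AE rates. It needs no extra tests or patients and changes no dose rule.

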8.2.2. Serious Adverse Events

An AE that meets one or more of the following criteria/outcomes is classified as a serious /ae (SAE):

- Results in death
- Is life-threatening (i.e., at immediate risk of death)
- Requires in patient hospitalization or prolongation of existing hospitalization.
- Results in persistent or significant disability/incapacity
- Results in congenital anomaly/birth defect
- Other Important Medical Events that may not result in death, be life-threatening, or require hospitalization may be considered serious when, based upon appropriate medical judgment, they may jeopardize the patient or may require medical or surgical intervention to prevent one of the outcomes listed above. Examples of such events are intensive treatment in an emergency room for allergic bronchospasm; blood dyscrasias or convulsions that do not result in hospitalization; or the development of drug dependence or drug abuse.

Serious also includes any other AE that the Investigator or sponsor judges to be serious, or which is defined as serious by the Health Regulatory Authority (HRA) in the country in which the event occurred.

Progression of the malignancy under study (including signs and symptoms of progression) should not be reported as an SAE unless the outcome is fatal during the study or within the safety reporting period for the study. Hospitalizations due to signs and symptoms of disease progression should not be reported as SAEs. However, if the malignancy has a fatal outcome

during the study or within the safety reporting period for the study, then the AE leading to death must be recorded as an SAE with CTCAE Grade 5.

The onset date of an SAE is defined as the date on which the event initially met serious criteria (e.g., the date of admission to a hospital). The end date is the date on which the event no longer met serious criteria (e.g., the date the patient was discharged from a hospital).

8.2.2.1. Hospitalization

AEs associated with in-patient hospitalization, or prolongation of an existing hospitalization, are considered serious. Any initial admission, even if the duration is less than 24 hours, is considered serious. In addition, any transfer within the hospital to an acute/intensive care unit is considered serious (e.g., transfer from the psychiatric wing to a medical floor or transfer from a medical floor to a coronary care unit). However, the following hospitalizations **should not** per se constitute a serious AE:

- Rehabilitation facility admission
- Hospice facility admission
- Respite care
- Skilled nursing facility admission
- Nursing home admission
- Emergency room visit, including observation unit visit
- Outpatient same day surgery/procedure
- Hospitalization or prolongation of hospitalization in the absence of precipitating clinical adverse events as follows:
 - Admission for treatment of preexisting condition not associated with the development of a new AE or with a worsening of the preexisting condition
 - Social admission
 - Administrative admission (e.g., for yearly physical exam)
 - Protocol-specified admission during a clinical trial
 - Optional admission not associated with a precipitating clinical adverse event (e.g., for elective cosmetic surgery)
 - Preplanned treatments or surgical procedures that are not related to an SAE
- Diagnostic and therapeutic noninvasive and invasive procedures, such as surgery, should not be reported as AEs. The medical condition for which the procedure was performed should be reported if it meets the definition of an AE (e.g., acute appendicitis that begins during the AE reporting period should be reported as an AE and the appendectomy should be recorded as a concomitant treatment).

8.3. Reporting Adverse Events

8.3.1. Eliciting Adverse Event Information

The Investigator is to report all directly observed AEs and all AEs reported by the study patient using concise medical terminology. In addition, each study patient will be questioned about AEs at each clinic visit following initiation of treatment. The question asked will be, or words to the effect, "Since your last clinic visit have you had any health problems?"

8.3.2. Adverse Event Reporting Period

Safety information for each patient will be collected from the date of informed consent. AEs occurring prior to the initiation of the study treatment with Abemaciclib study drug will be considered "baseline-emergent adverse events," will be recorded on corresponding CRFS and will not be retained for patients who fail screening. The AE reporting period for this study begins when the patient has received even a portion of the first dose of Abemaciclib study drug and ends 28 days after the last dose of the latest study treatment (i.e., Abemaciclib study drug) is administered.

All AEs that occur in study patients during the AE reporting period specified in the protocol must be reported to ELI LILLY, whether or not the event is considered study treatment-related. In addition, any known untoward event that occurs beyond the AE reporting period that the Investigator assesses as possibly related to either investigational medication/product should also be reported as an AE.

